16.2.1.1 Severity

Severity is classified as mild/ moderate/ severe. AEs with a missing severity will be counted in a separate missing category. If a patient reports an AE more than once within that SOC/ PT, the AE with the worst case severity will be used in the corresponding severity summaries.

16.2.1.2 Relationship to Study Medication

Relationship, as indicated by the Investigator, is classed as "Unassessable/Unclassified", "Conditional/Unclassified", "Unrelated", "Unlikely", "Possible", "Probable", and "Certain". Adverse events with a relationship of "Possible", "Probable" and "Certain" to IMP will be considered as related to study medication. AEs with a missing relationship to study medication will be counted in a separate missing category. If a patient reports the same AE more than once within that SOC/ PT, the AE with the worst case relationship to study medication will be used in the corresponding relationship summaries.

16.2.2 ADVERSE EVENTS LEADING TO DOSE CHANGE OR DISCONTINUATION OF STUDY MEDICATION

If the action taken for an AE is recorded as "IMP permanently discontinued" on AE page of the CRF it will be considered as an AE leading to permanent discontinuation. If the action taken for an AE is recorded as "IMP dose changed" on AE page of the CRF it will be considered as an AE leading to dose change. These will be summarized by SOC and PT by treatment sequence group and also listed.

16.2.3 SERIOUS ADVERSE EVENTS

SAEs are those events recorded as "Serious" on the Adverse Events page of the CRF. A summary of SAEs by SOC, PT and severity, as well as a summary of related SAEs by SOC, PT, and severity will be reported by treatment sequence group. The tables will be repeated for serious adverse events during the 4 hour post doing period. Summaries will also be provided for SAEs leading to dose change as well as study discontinuation. These data will also be listed.

16.2.4 ADVERSE EVENTS LEADING TO DEATH

AEs leading to Death are those events with outcome reported as "Fatal" in the Adverse Events page of the CRF. A summary of AEs leading to death by SOC and PT will be prepared. This information will also be listed.

16.3 DEATH

As only AEs leading to death are recorded for this study, please refer to Section 16.1.4.

16.4 LABORATORY EVALUATIONS

Clinical assessments on hematology and clinical chemistry are to be measured at Visit 1 and Visit 3 (Early Termination Visit). A list of laboratory assessments to be included in the outputs is provided in appendix 1.

Local laboratories will be used for the assessment of hematology and clinical chemistry data and these data will be converted to the International System (SI) of units by Data Management Team using standard conversion factors. Quantitative laboratory measurements reported as “ $< X$ ”, i.e. below the lower limit of quantification (BLQ), or “ $> X$ ”, i.e. above the upper limit of quantification (ULQ), will be converted to X for the purpose of quantitative summaries, but will be presented as recorded, i.e. as “ $< X$ ” or “ $> X$ ” in the listings.

At each visit, summary statistics for the absolute laboratory value and the changes from baseline will be presented by treatment sequence group and overall. The significance of changes from baseline will be assessed using the Wilcoxon Signed-Rank Test within each sequence group and overall.

Each pre-study baseline laboratory value will be categorised as low, normal, or high based on the reference range:

Low: Below the lower limit of the laboratory reference range.

Normal: Within the laboratory reference range (upper and lower limit included).

High: Above the upper limit of the laboratory reference range.

Each post-baseline value will be classified in a similar manner, producing a 3×3 table for each treatment sequence group at each post-baseline visit. Scores of “1” will be assigned to low values, “2” to normal values, and “3” to high values. Using these scores, shifts from baseline will also be assigned a score. For example, a laboratory value that shifts from low to high will be assigned a score of 2, whilst a laboratory value that remains at a low value will be assigned a score of 0. Shifts between these categories between baseline and Visit 3 (Early Termination Visit) will be compared using the Wilcoxon Signed-Rank test within each treatment sequence group and overall. Statistical testing will be performed at last visit.

In addition to the high and low quantitative laboratory assignments (as identified by means of the laboratory reference ranges), clinically significant quantitative laboratory assessments will be identified by investigator and the result will be recorded in the CRF. The number and percentage of patients with abnormal or clinically significant results will be tabulated by treatment sequence groups by visit. The results will also be listed.

Women of child-bearing potential will undergo urine pregnancy testing (positive or negative). The results will be listed.

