A similar study was previously conducted in China to demonstrate the effect of Gaviscon® Original Liquid on esophageal pH in GERD patients [9]. No clinical studies have been performed with Compound Sodium Alginate Double Action Chewable Tablets to demonstrate the effect on esophageal pH in patients with GERD. This study is being conducted to provide evidence for inclusion in applications to regulatory authorities that Compound Sodium Alginate Double Action Chewable Tablets are effective for the treatment of reflux in patients diagnosed with GERD.

The potential risks to patients taking part in the present study are considered to be low. Endoscopy and placement of the pH catheter can cause discomfort but the risks associated with these procedures are considered to be low. The adverse reactions that occur very rarely (<1/10,000) as a result of taking Gaviscon® products are allergic manifestations such as urticaria or bronchospasm, anaphylactic or anaphylactoid reactions as a result of a patient being sensitive to any of the active substances (sodium alginate, sodium bicarbonate and calcium carbonate) or any of the excipients. Other adverse reactions include:

1. Sodium bicarbonate – increased plasma sodium levels especially for those with renal and cardiovascular conditions on a highly restricted salt diet.
2. Calcium carbonate – high doses of calcium may cause alkalosis, hypercalcaemia, acid rebound, milk alkali syndrome or constipation.

For this reason, the risk benefit balance for the current study is considered to be acceptable.

This study will be conducted in accordance with the principles set out in the Declaration of Helsinki. It will comply with International Conference on Harmonisation (ICH) Good Clinical Practice (GCP) and applicable regulatory requirements.

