- 2) The Investigator will conduct 4-hour pH monitoring (see section 11.3.2.1 4-hour pH monitoring for procedure and fasting requirements). At this second dosing visit, the patient will receive the alternate randomised study treatment (four Compound Sodium Alginate Double Action Chewable Tablets or four matching placebo tablets).
- 3) 4-hour pH monitoring data will be collected from Visit 3. The Investigator will record any additional adverse events and concomitant medications at the end of the visit.
- 4) All medication, used and unused blister packs, will be returned to the drug dispensing unit.

Post study Follow Up Assessments (visit 3)

The following examinations and investigations will be conducted after the pH monitoring data has been collected (on the same day as the pH monitoring visit):

Vital Signs

- Blood pressure (after sitting for 5 minutes; mmHg).
- Heart rate (radial pulse counted for 30 seconds after resting for 5 minutes; beats/minute).

Concomitant Medication

- All concomitant medication usage including any OTC medications and traditional Chinese medications will be recorded.

Adverse Events

- All adverse events will be recorded.

Physical examination

- A standard physical examination will be conducted.

Laboratory investigations (haematology and clinical chemistry)

- Details are listed in section 13.4.

Pregnancy testing

- Women of child-bearing potential will undergo urine pregnancy testing.

11.3.2.3 Clinical Assessments at Early Termination (ET) Visit (only if required for patient early terminations)

If the investigator withdraws the patient from the study for any reason after Visit 2 the patient will complete the study at this early termination visit and the following will be completed.

Vital Signs

- Blood pressure (after sitting for 5 minutes; mmHg).
- Heart rate (radial pulse counted for 30 seconds after resting for 5 minutes; beats/minute).

Concomitant Medication

- All concomitant medication usage including any OTC medications and traditional Chinese medications will be recorded.

Adverse Events

- All adverse events will be recorded.

Physical examination

- A standard physical examination will be conducted.

Laboratory investigations (haematology and clinical chemistry)

- Details are listed in section 13.4.

Pregnancy testing

- Women of child-bearing potential will undergo urine pregnancy testing

Early Study Termination

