14.5.2 Laboratory Data

For the purpose of analysing laboratory data, "baseline" is defined as the baseline assessments at Visit 1, screening and "last visit" is defined as the final visit, Visit 3 or the Early Termination Visit.

Each pre-study baseline laboratory value will be categorised as low, normal, or high based on the reference range. Each post-baseline value will be classified in a similar manner, producing a 3 x 3 table for each treatment group at each post-baseline visit. Scores of "1" will be assigned to low values, "2" to normal values, and "3" to high values. Using these scores, shifts from baseline will also be assigned a score. For example, a laboratory value that shifts from low to high will be assigned a score of 2, whilst a laboratory value that remains at a low value will be assigned a score of 0. Shifts between these categories between baseline and subsequent timepoints will be compared using the Wilcoxon Signed-Rank test within each treatment group. Statistical testing will be performed at last visit.

At each visit, summary statistics for the absolute laboratory value and the changes from baseline will be presented by treatment group. The significance of changes from baseline will be assessed using the Wilcoxon Signed-Rank Test.

Scatter plots of end of treatment values versus baseline values will be provided for all laboratory tests.

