16.6 VITAL SIGNS

Vital signs will be conducted at baseline and final or early termination visits. The following Vital Signs measurements will be reported:

Systolic and diastolic blood pressure (after sitting for 5 minutes; mmHg)

Heart rate (radial pulse counted for 30 seconds after resting for 5 minutes; beats/minute)

At each visit, summary statistics for the absolute vital sign value and the changes from baseline will be presented by treatment sequence group and overall. The significance of changes (within each sequence separately and overall) from baseline will be assessed at the last visit, using the Wilcoxon Signed-Rank Test.

A complete listing on all patients' vital sign result will be presented.

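### Laboratory and vital-sign changes are tested within each sequence and overall, but never between sequences, so the one randomised active-versus-placebo contrast at Visit 3 is left unused

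*SAP*

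**What the plan says.** **Sampling times.** For laboratory data SAP 16.4 says: "Clinical assessments on hematology and clinical chemistry are to be measured at Visit 1 and Visit 3 (Early Termination Visit". For vital signs SAP 16.6 says: "Vital signs will be conducted at baseline and final or early termination visits". Protocol 11.3.2.2 places the Visit 3 assessments within the day: they "will be conducted after the pH monitoring data has been collected (on the same day as the pH monitoring visit"). Nothing is scheduled after the Visit 2 dose.

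**Dose at that visit.** SAP 7.1 defines Group A as active at Visit 2 and placebo at Visit 3, and Group B as the reverse.

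**Planned tests.** The laboratory sentence in SAP 16.4 is "The significance of changes from baseline will be assessed using the Wilcoxon Signed-Rank Test within each sequence group and overall". The low/normal/high shift scores are tested in the same three groupings. For vital signs SAP 16.6 has "The significance of changes (within each sequence separately and overall) from baseline will be assessed at the last visit". Summary statistics are by sequence and overall, and abnormal and clinically significant laboratory counts are by sequence. No table listed in SAP 17 is described as comparing the two sequences on these data.

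**Protocol.** Section 14.5.2 speaks of treatment groups, "producing a 3 x 3 table for each treatment group at each post-baseline visit", but it too plans only within-group tests.

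**The concern.** A within-sequence test of change from screening has no control. Visit 3 blood is drawn after a fast and a 990 kcal test meal containing 124 g of carbohydrate (Protocol 12.5). Protocol 11.3.1.1 states no fasting condition for screening blood. Glucose, urea and inorganic phosphorus are in the panel, so a shift unrelated to the Visit 3 dose is plausible in both sequences.

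Two misreadings follow. A change common to both sequences may be taken for a drug effect. And if one sequence is significant and the other is not, that may be taken for a treatment difference, which it is not. The overall test adds a third problem, because it averages patients just dosed with active and patients just dosed with placebo.

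Protocol 6 lists raised plasma sodium as a possible reaction and, for calcium carbonate, says that "high doses of calcium may cause alkalosis, hypercalcaemia, acid rebound, milk alkali syndrome or constipation". Sodium and calcium are both measured. The randomisation supplies a concurrent placebo group for any acute effect on them, and the plan does not use it.

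**Working it through.** **1. What each sequence has received at the Visit 3 sample.** Recording stops 4 h after dosing (Protocol 9.6), and the sample follows on the same day. The clock time is not fixed, so about 4 h or later is an inference.

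| | Group A | Group B |
|---|---|---|
| Visit 3 dose | placebo | active |
| Time since last active tablet | at least 24 + 4 = 28 h | about 4 h or more |
| Time since end of test meal | about 0.5 + 4 = 4.5 h or more | same |
| Preceding week | open-label active | open-label active |

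The 24 h comes from Protocol 9.6.1, under which the between-visit tablets stop at least 24 h before Visit 3. By design, the main difference at this sample is the Visit 3 dose.

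**2. Count of planned tests.** Protocol 13.4 and SAP Appendix 1 list 5 haematology and 10 chemistry analytes. SAP 16.6 lists systolic pressure, diastolic pressure and heart rate.

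- Laboratory: 15 analytes × 2 (change, shift) × 3 (A, B, overall) = 90.
- Vital signs: 3 × 3 = 9.
- Total 99. At the 5% level of SAP 6.4, about 99 × 0.05 = 4.95 would be significant if nothing changed. None contrasts active with placebo.

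**3. What each analysis estimates.** Let c be the change common to both sequences and d the acute effect of the Visit 3 active dose. The mean change is c in Group A and c + d in Group B. With equal sequences the overall mean is c + d/2, while Group B minus Group A is d.

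**4. How the tests behave.** Simulation with normal data, SD of change 1, 18 per sequence, 3000 runs; the table gives the percentage significant at 5%.

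| c, d (SD) | Within A | Within B | Overall | Exactly one sequence | B versus A (rank-sum) |
|---|---|---|---|---|---|
| 0.5, 0 | 50 | 51 | 82 | 50 | 5 |
| 0, 0.8 | 5 | 87 | 57 | 83 | 61 |
| −0.4, 0.8 | 34 | 35 | 3 | 44 | 61 |

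In the first row there is no acute effect, yet the overall test is usually significant, and half the time just one sequence is. In the third row there is a real acute effect and the overall test almost never shows it.

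**5. Precision of the missing contrast.** The documents give no SD, so results are in SD of change. They state no allocation ratio, so 1:1 is assumed. The sizes of 36 completing and 44 enrolled are in Protocol 14.1, which gives no statistical derivation to reproduce.

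95% CI half-width = t(0.975, 2n − 2) × √(2/n):

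- n = 18: 2.032 × 0.3333 = 0.68 SD.
- n = 22: 2.018 × 0.3015 = 0.61 SD.

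Difference detectable with 80% power, normal approximation = (1.960 + 0.842) × √(2/n): 0.93 SD for n = 18 and 0.85 SD for n = 22. Power at 0.5 SD is 0.32 and 0.38 respectively.

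**The case against.** The strongest reply is that the plan already shows what is needed. At Visit 3 the sequence identifies the dose, so the by-sequence columns set after-active beside after-placebo. A meal or fasting effect would show in the Group A column, and the within-B test sees an acute effect undiluted: with no common shift it detects 0.8 SD 87% of the time, against 61% for the between-sequence test. This stands as a description of the display. It does not supply the comparison, because two within-group p-values do not estimate a difference, and the within-B advantage depends on there being no common shift.

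A reader might infer that the SAP merges the sequences and loses the distinction. It does not: the overall result is additional to results within each sequence, and only that extra result carries the half-size dilution. A reader might also infer that an electrolyte hazard would go unseen. The documents do not support that either. Investigators flag clinically significant values, which are tabulated by sequence. Protocol 6 ties hypercalcaemia and alkalosis to high calcium doses, and raised sodium especially to renal and cardiovascular patients on a salt-restricted diet. Known hypercalcaemia, damaged heart or kidney function and a need for a low-sodium diet are exclusions, and Protocol 13.1.8 describes the active drug as not absorbed. Alkalosis cannot be assessed directly in any case, because the panel has neither bicarbonate nor blood pH.

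Other limits also stand. The no-food-or-drink rule is worded for the first dosing visit and reaches Visit 3 only by cross-reference. Visit 1 may fall on the same day as Visit 2, so some screening samples may be fasted. SAP 6.3 maps early-termination samples to the next visit, and they are not post-dose samples of this kind. Restricting to patients dosed at Visit 3 is a selection made after randomisation. The fix adds 15 + 3 = 18 wide intervals to a set with no multiplicity adjustment. These points limit what the contrast can show, but they do not justify leaving it out.

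**Conclusion.** The gap is real and minor. All 99 planned signed-rank tests are uncontrolled, and none estimates the acute effect of active against placebo, although one sample per patient allows it. The missing contrast would have a 95% CI half-width of about 0.61 to 0.68 SD, so it is useful as an estimate and weak as a test.

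This rests on four assumptions: roughly equal sequences; sampling soon after the recording ends; few losses before the Visit 3 dose; and no lasting effect of the single Visit 2 dose, which differs between the sequences and was taken about a week earlier. The contrast says nothing about the week of open-label tablets, which both sequences took and which has no control in either. The primary endpoint is unaffected.

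**What to change.** In SAP 16.4 and 16.6:

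- Add the Group B minus Group A difference in change from screening to Visit 3 for each analyte and vital sign, with a 95% CI (t-based or Hodges-Lehmann).
- Restrict it to patients dosed at Visit 3, and exclude early-termination samples mapped to that visit.
- Label it the acute single-dose active-versus-placebo contrast. Report it as an estimate, and say that a non-significant result is not evidence of no effect.
- Treat the overall signed-rank tests as descriptive, with a footnote that the Visit 3 dose differs by sequence.
- State that the week of open-label tablets has no control in either sequence.

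The cost is one column in existing tables and a footnote, with no new samples. The downside is a wide parallel-group comparison of about 18 to 22 per sequence. If the contrast is added after database lock, record it as unplanned.

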16.5 ECG EVALUATIONS

A 12-lead ECG examination will be conducted at baseline. The results will be listed and summarised as per Section 10.

Document: Reckitt Benckiser GA1202 Statistical Analysis Plan

Author: [REDACTED]

Version Number:

Final 5.1

Version Date:

[25Feb2014]

Template No: CS_TP_BS016 – Revision 3

Effective Date: 01May2012

Reference: CS_WI_BS005

Page 22 of 29

16.6 VITAL SIGNS

Vital signs will be conducted at baseline and final or early termination visits. The following Vital Signs measurements will be reported:

Systolic and diastolic blood pressure (after sitting for 5 minutes; mmHg)

Heart rate (radial pulse counted for 30 seconds after resting for 5 minutes; beats/minute)

At each visit, summary statistics for the absolute vital sign value and the changes from baseline will be presented by treatment sequence group and overall. The significance of changes (within each sequence separately and overall) from baseline will be assessed at the last visit, using the Wilcoxon Signed-Rank Test.

A complete listing on all patients' vital sign result will be presented.

16.7 PHYSICAL EXAMINATION

A physical examination is to be performed at Visit 1 and Visit 3 or early termination visit. The following summaries will be provided for physical examination data:

Incidence of clinically significant abnormalities at screening

Incidence of clinically significant abnormalities at Visit 3 (early termination visit)

A shift table on clinically significant abnormalities between baseline and Visit 3 (Early Termination Vist) will be presented, and P- values from McNemar's test will be reported within each sequence group and overall.

A listing on clinical significant abnormalities will be reported.

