10 STUDY POPULATION

10.1 Inclusion Criteria

Only patients to whom all of the following conditions apply will be included:

1. Informed consent has been obtained.
2. Age: ≥ 18 years to ≤ 65 years.
3. Sex: male or female.
4. Primary diagnosis: meet the diagnostic criteria for GERD with a GERD history of frequent episodes of GERD-related symptoms during the last 2 months prior to study screening. The patient must also meet the following criteria:
 - a. The only or main symptom is heartburn (burning feeling back of breast bone) and/or acid reflux. Symptoms persists or have occurred repeatedly for more than 2 months;
 - b. As assessed by the Investigator at screening by questioning of the patient, the frequency of occurrence of heartburn is ≥ 3 days/week and the score of severity of heartburn in general is \geq Level 2 within 3 weeks before screening;

The severity of heartburn will be evaluated as follows:

Level 0	no heartburn
Level 1	heartburn is mild in severity and is not obvious
Level 2	heartburn is moderate, or it is obvious when it occurs, the patient experiences discomfort
Level 3	heartburn is severe and significant, seriously interferes with daily activities

The frequency of heartburn will be evaluated as number of days /week that heartburn is suffered (0, 1, 2, 3, 4, 5, 6 or 7 days).

5. Status: Patients will be patients at the clinic or members of the public who respond to an advertisement or via their doctor.
6. Patients who have not taken any antacids within 24 hours before randomisation (Visit 2) and be instructed not to take antacids, other than the Compound Sodium Alginate Double Action Chewable Tablets provided, throughout the remainder of the study.
7. Patients taking mucous membrane protection drugs or prokinetics may enter the study provided that these are discontinued for at least 5 days before screening and throughout the remainder of the study.
8. Systemic glucocorticosteroids or non-steroidal anti-inflammatory drugs (NSAIDs, except for low dose aspirin which can be given for cardioprotection) can only be taken for up to 3 consecutive days in the 28 days prior to screening.
9. Absence of relevant abnormalities in the physical examination, endoscopy, ECG and laboratory safety results.
10. Patients who are willing to consume the entire standard refluxogenic test meal.
Patients cannot be vegetarian.

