3. STUDY DESIGN

3.1. GENERAL DESCRIPTION

This is a multi-centre, randomised, open-label, placebo-controlled, two-period crossover study. Forty - four (44) patients are planned to be enrolled in this study to ensure that thirty six (36) patients complete it. After signing a written informed consent, patients will undergo a screening period up to 10 days. Patients who satisfy the study entry requirements within 10 days of consent, will be randomised to receive either four Compound Sodium Alginate Double Action Chewable Tablets or four matching placebo tablets following placement of a pH electrode and a standardised refluxogenic meal.

Upon completion of the 4-hour post-dose pH monitoring period patients will be instructed to begin taking supplied Compound Sodium Alginate Double Action Chewable Tablets (two tablets four times daily) for 7 days. Patients will return after the 7 day period for repeat catheter insertion and pH monitoring, receiving the alternative randomised treatment.

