5.2. SAFETY POPULATION

All patients who are subjected to any invasive procedures and/or take at least one dose of study medication will be included in safety population.

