6.2. BASELINE

Unless otherwise specified, baseline value refers to the tests or measurements recorded at Visit 1, screening visit. If a particular test or measurement was repeated after Visit 1, screening visit, then the baseline value is defined as the last non-missing measurement taken prior to Visit 2, Day 0 (including unscheduled assessments). In the case where the last non-missing measurement and the reference start date coincide, that measurement will be considered pre-baseline, but Adverse Events (AEs) and medications commencing on the reference start date will be considered post-baseline.

For patients randomized but not treated, baseline is defined as the last non-missing measurement taken on or before the baseline visit date.

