6.4. STATISTICAL TESTS

The default significant level will be (5%); confidence intervals (CIs) will be 95% and all tests will be two-sided, unless otherwise specified in the description of the analyses.

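### The McNemar p-value for the physical-examination shift cannot be interpreted, because eligibility leaves almost only normal-to-abnormal shifts and there is no concurrent control

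*SAP*

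**What the plan says.** SAP 16.7 lists three summaries of the physical examination: incidence of clinically significant abnormalities at screening, incidence at Visit 3 or early termination, and a baseline-to-Visit 3 shift table. For the shift table, p-values from McNemar's "test will be reported within each sequence group and overall". The output is Table 14.3.5.2, on the Safety population.

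Four other places bear on it:

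- **Eligibility.** Protocol 10.1, criterion 9 (repeated in synopsis 3.8), requires "Absence of relevant abnormalities in the physical examination, endoscopy, ECG and laboratory safety results".
- **Baseline.** Under SAP 6.2, unless otherwise specified, the "baseline value refers to the tests or measurements recorded at Visit 1, screening visit". The Protocol's Table 11-1 schedules a physical examination at Visit 1 and Visit 3 but not at Visit 2, so the eligibility examination and the baseline examination are the same one.
- **Error level.** SAP 6.4 sets 5% by default, and "all tests will be two-sided, unless otherwise specified". It does not say whether McNemar's test is exact or asymptotic.
- **Numbers.** SAP 3.1: "Forty - four (44) patients are planned to be enrolled in this study to ensure that thirty six (36) patients complete it".

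**The concern.** McNemar's test uses only the patients who change category. Its null is that a change from normal to abnormal is as likely as a change from abnormal to normal. That represents no effect when patients enter without regard to the variable tested. Here they are admitted because they lack relevant abnormalities at the examination that serves as baseline. Almost nobody can improve, while anyone can acquire a finding for reasons unrelated to the product. The null would then be false even for an inert tablet.

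The design offers no comparison that would repair this. The Visit 3 examination takes place after the second pH session (Protocol 11.3.2.2). By then completers in both sequence groups have taken the active dose, the placebo dose and about a week of active non-investigational tablets (SAP 14). Neither the within-sequence p-values nor the overall one separates product from placebo or from the passage of time.

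What is at stake is one column of a safety table. A small p-value could be read as a signal of harm and a large one as reassurance, and neither reading would be justified.

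**Working it through.** **Plan's own figure.** There is none to reproduce. The documents state no power, error rate or expected count for this test, and Protocol 14.1 says that the sample size has no statistical justification.

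**Inputs.** Two-sided 5% (SAP 6.4). Pairs: 36 planned completers, with 44 enrolled as an upper bound because early-termination examinations also count (SAP 3.1 and 16.7). About 18 to 22 per sequence, assuming equal allocation. The chance π that a patient normal at baseline has a new clinically significant abnormality at Visit 3 without any product effect is not given, so a range is assumed.

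**Step 1: how many new abnormalities give p < 0.05.** Let b be the normal-to-abnormal count and c the abnormal-to-normal count, with c = 0.

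- Exact: p = 2 × 0.5^b. b = 5 gives 0.0625; b = 6 gives 0.031.
- Asymptotic: chi-square = (b − c)²/(b + c) = b on 1 df. b = 3 gives p = 0.083; b = 4 gives 0.0455.
- Continuity-corrected: chi-square = (b − 1)²/b. b = 5 gives p = 0.074; b = 6 gives 0.041.

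The threshold is thus 4 (asymptotic) or 6 (exact or corrected), whether overall or within one sequence group.

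**Step 2: chance of reaching it with no product effect.** This is P(Bin(n, π) ≥ 4) or P(Bin(n, π) ≥ 6). For example, with n = 36 and π = 0.05, the chances of 0, 1, 2 and 3 events are 0.158, 0.299, 0.275 and 0.164. They sum to 0.896, so the asymptotic test rejects with probability 0.104.

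| Assumed π | n = 36, asymptotic / exact | n = 44, asymptotic / exact |
|---|---|---|
| 1% | <0.1% / <0.1% | 0.1% / <0.1% |
| 2% | 0.6% / <0.1% | 1.1% / <0.1% |
| 5% | 10% / 0.8% | 18% / 2% |
| 8% | 32% / 6% | 47% / 14% |
| 10% | 49% / 15% | 65% / 27% |

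Rejection passes 5% at π of about 3.9% (n = 36) or 3.2% (n = 44) for the asymptotic test, and about 7.5% or 6.1% for the exact test. Within one sequence group of 18 or 22, π = 10% gives 9.8% or 17% asymptotic and 0.6% or 1.8% exact.

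**Step 3: is selection the cause?** Take an unselected cohort with the same prevalence at both visits and independent visits. At 5% prevalence the asymptotic test rejects in 3.7% (n = 36) or 4.4% (n = 44); at 10% it rejects in 4.7% or 4.4%. The exact test stays below 2%. The excess in the table therefore comes from selection on the baseline examination.

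**Step 4: if the abnormal-at-baseline row is not quite empty.** Let one patient on average be abnormal at baseline (probability 1/n, independent visits). At π = 5%, rejection becomes 4.3% / 0.3% (n = 36) or 7.1% / 0.9% (n = 44). At 10% it becomes 22% / 7% or 32% / 13%. The inflation shrinks but remains at the higher rate.

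**Step 5: the rare end.** With no patient changing category the statistic is 0/0. That has probability (1 − π)^n: 0.70 (n = 36) or 0.64 (n = 44) at π = 1%, and 0.48 or 0.41 at 2%.

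**The case against.** The strongest reply is that the test will probably never mislead anyone. Participation lasts at most 19 days (Protocol 9.5), and four or six new clinically significant findings in so short a time may be unlikely. At 1% to 2% the likely result is non-significant or not computable. SAP 16.7 already supplies both incidences, the shift table and a listing, so a reader will see the nearly empty row beside the p-value. No decision rule hangs on it. All of this stands, and it keeps the point minor. It does not make the p-value meaningful: a result that is inflated when findings are common and empty when they are rare informs in neither case.

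The second reply is that the abnormal-at-baseline row need not be empty. This also stands. Criterion 9 speaks of relevant abnormalities and SAP 16.7 of clinically significant ones, and nothing equates the two. The Safety population, "All patients who are subjected to any invasive procedures and/or take at least one dose of study medication", is defined without reference to eligibility, so patients entered in violation can remain. The SAP itself plans to tabulate "Incidence of clinically significant abnormalities at screening". A reader might infer that shifts can go only one way; the documents support nearly one way.

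A reader might also infer that selection by itself makes the test reject, or that any background rate will in time do so. Neither follows. Rejection needs the counts in Step 1, the documents give no rate, and the sample is fixed with no replacement of withdrawals (Protocol 11.7.2). Nor is the p-value unrelated to treatment: a harmful product would raise b. The trouble is that background findings raise b too, and nothing in this table tells the two apart.

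**Conclusion.** The concern holds as a minor safety-table point. The equal-shift null is not a no-effect null in patients selected on the baseline examination, and the before/after comparison has no concurrent control, so the p-value cannot be interpreted whichever way it falls.

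The direction of the error depends on a rate that the documents do not give. Above roughly 3–4% new findings (asymptotic) or 6–8% (exact), false rejection exceeds the nominal 5%. Below that the test seldom rejects, and at the lowest rates it often cannot be computed. These figures assume no abnormal-to-normal shifts, independent patients and 36 to 44 pairs; a few abnormal baselines would soften them, as Step 4 shows. The documents do not support a prediction that the test will in fact reject. Efficacy conclusions are not affected.

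**What to change.** Delete the McNemar p-values from SAP 16.7 and Table 14.3.5.2. Keep the planned incidences, shift table and listing. Add, overall and by sequence group, the number and percentage of patients normal at baseline who have a new clinically significant abnormality at Visit 3 or early termination, with an exact 95% confidence interval. With no events the upper limit is 1 − 0.025^(1/n), which is 9.7% for 0 of 36 and 8.0% for 0 of 44. That tells the reader how much the data can exclude, which the p-value does not.

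The cost is a change of SAP wording and one table column, with no new data. The downside is that a supportive safety p-value disappears. The Protocol did not promise it: section 14.5 plans no test of physical-examination findings, and 14.5.4 rules out analysis of further safety variables.
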